5.8.2. Helminthiasis

Treatment for helminthiasis, with mebendazole or albendazole, will be provided free of charge by the Sponsor for use as per usual practice in the investigational centres.

Treatment for helminthiasis will be followed by a recovery period of at least 3 days between the last dose of the antimalarial agent and the first administration of treatment for HAT, as per usual practice in the investigational centres.

5.8.3. Contraception

Women of child-bearing potential will be advised to use a method of contraception or to abstain from sexual relations during the treatment period and, if possible, until cure is confirmed. Medically proven methods of contraception, i.e. hormonal contraception and condoms, will be available to patients free of charge during the 24-month follow-up period.

5.8.4. Other Medication

Unless there is an urgent medical need, patients should refrain from using any medication required to treat concurrent conditions until after the end of the treatment for HAT.

Any medication used during the hospitalisation period must be recorded in the e-CRF, specifying the reason for use.

Information on any serious adverse event (SAE) that may occur during the followup period will be collected at an unscheduled visit and recorded in the e-CRF, specifying any treatment(s) received. Other medical events will be recorded only in the patient's medical file.

Any essential medicine required during the 24-month follow-up period in the study will be provided to the patient free of charge. The WHO List of Essential Medicines and the MSF reference guide entitled *Essential Medicines* (2010 edition) will be used as a basis for treatment of any concurrent condition. For any chronic condition, the study team will take all necessary measures to ensure that the patient is referred to the most appropriate healthcare facility in the region.

5.9. Rescue Treatment

Patients who show no clinical response to treatment at the EOT visit, as well as patients with evidence of relapse, i.e. *T.b. gambiense* found in any bodily fluid, or of probable relapse at any time during follow-up will receive an alternative treatment for HAT, as per usual practice in the investigational centre.

Rescue treatment for HAT will not be recorded as concomitant treatment in the e-CRF, but will be recorded in the Comments section with the date of treatment start.

Probable relapse at the 6-month, 12-month or 18-month follow-up visit is defined as follows:

Table 2 – Clinical Classification of Patients

Visit	Ideal timing of visit after end of treatmen t	Favourable outcome	Uncertain outcome	Probable relapse	Proven relapse
24 hours after EOT	Within 2 days	 Patient alive with no evidence of trypanosomes in any bodily fluid (54) 			 Evidence of trypanosomes in any bodily fluid
3 months	3 months ± 1 week	 Patient alive with no evidence of trypanosomes in any bodily fluid (no lumbar puncture at 3 months unless Investigator suspects relapse) 	Any reason prompting the Investigator to request an additional follow-up visit	 Neurological signs or symptoms leading to use of rescue treatment 	 Evidence of trypanosomes in any bodily fluid
6 months	6 months ± 2 weeks	 Patient alive with no evidence of trypanosomes in any bodily fluid and CSF WBC ≤ 20/µL 	 CSF WBC between 20 and 50/µL and additional visit requested within 1- 3 months Any reason prompting the Investigator to request an additional follow-up visit 	 CSF WBC ≥ 50/µL (36) Neurological signs or symptoms leading to use of rescue treatment 	• Evidence of trypanosomes in any bodily fluid
12 months	12 months ± 4 weeks	 Patient alive with no evidence of trypanosomes in any bodily fluid and CSF WBC ≤ 20/µL CSF WBS between 20 and 50/µL, and lower as compared to previous value(s) 	 CSF WBC > 20/µL and non- significant increase from a clinical standpoint in relation to prior value(s) Any reason prompting the Investigator to request an additional follow-up visit 	 CSF WBC ≥ 20/µL CSF WBC > 20/µL and significant increase from a clinical standpoint in relation to prior value(s) Neurological signs or symptoms leading to use of rescue treatment 	• Evidence of trypanosomes in any bodily fluid
18 months and 24	18 months ± 4 weeks 24 months ± 4 weeks	 Patient alive with no evidence of trypanosomes in any bodily fluid and CSF WBC ≤ 20/µL Patients with no signs of HAT and refusing to undergo 	 Any reason prompting the Investigator to request an additional follow-up visit 	 CSF WBC > 20/µL Neurological signs or symptoms leading to use of rescue treatment 	 Evidence of trypanosomes in any bodily fluid
24 months		lumbar puncture and who, in the opinion of the Investigator do not require rescue treatment or an additional follow-up visit			

An uncertain outcome may be a discrepancy between the clinical picture and the laboratory findings, or any situation that leads the Investigator and the study team to consider that an additional follow-up visit is required to decide whether or not to provide rescue treatment. This classification will not be used directly for statistical purposes.

6. Schedule of Study Procedures and Assessments6.1. Timing of Assessments

See Table 4 - Timing of Assessments (p 99)

- D-15 to D-1: Patient screening with detection of *T.b. gambiense*, pretreatment of concomitant malaria and/or helminthiasis, if any, ECG and laboratory screening tests
- D-4 to D-1: Baseline assessment
- D1 to D10: Treatment period
- D8 to D12: PK sampling for patients in the fexinidazole group
- D11: End-of-Treatment (EOT) visit
- between D13 and D18: End-of-Hospitalisation (EOH) visit; if hospitalisation is prolonged beyond D18, the EOH visit should be recorded on D18 and an unscheduled visit should take place at the actual time of discharge from hospital
- Additional Follow-up Visit: in Week 9 after D1, i.e. D64 to D70, for patients who reach this visit starting in mid-December 2014
- Follow-up Visits: at M3, M6, M12, M18 and M24 after D11, see Table 3 Theoretical Schedule of Visits and Acceptable Leeway). The timing of follow-up visits is calculated from D11 (EOT).

Theoretical schedule of visits	Ideal timing of visits	Acceptable leeway*	
End-of-Treatment visit (EOT)	D11 after the Start of Treatment (SOT) (D1 after EOT)	Between D11 and D12 after SOT (D1 or D2 after EOT)	
End-of-Hospitalisation visit (EOH)	Between D13 and D18 after SOT (D3 and D8 after EOT)	D18 at the latest	
Week 9 after D1	D64 to D70		
3 months	3 months ± 1 week after EOT	2-4 months after EOT	
6 months	6 months ± 2 weeks after EOT	5-9 months after EOT	
12 months	12 months ± 4 weeks after EOT	10-16 months after EOT	
18 months	18 months ± 4 weeks after EOT	17-21 months after EOT	
24 months	24 months ± 4 weeks after EOT	≥ 22 months after EOT	

Table 3 - Theoretical Schedule of Visits and Acceptable Leeway

*The acceptable leeway for the visits starts on the first day of the period mentioned and ends on the last day of the period mentioned.

For the purposes of the study, patients will be hospitalised from their arrival at the hospital/investigational centre until D18. They will be permitted to leave hospital from D13 onwards, if their clinical status allows it.

Any additional unscheduled visits that may take place must be recorded in the e-CRF.

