2.2.2. Secondary Efficacy Endpoints or Exploratory Endpoints Early Efficacy Endpoints

The early efficacy endpoints used in the futility and secondary analyses vary depending on the timepoint and analysis.

Futility analyses (FAs) assessing the response rate are planned in order to stop exposure to the IP if efficacy is below an acceptable limit (see Section 9.11 Futility Analyses; p 67).

All cases of probable relapse and all deaths will be included as relapses in all analyses.

Table 1 - Definitions of Early Efficacy Endpoints, for statistical purposes only

	Ideal		Responder /	Non-responder / Relapse	
Timepoint	timing of visit after EOT	Analyses	Favourable outcome	Probable Relapse	Confirmed Relapse
24 hours after EOT	Within 2 days	FA1 n ₁ =20 Fexi FA2 n ₂ =70 Fexi	• Patient alive with no evidence of trypanosomes in any bodily fluid (54)		• Evidence of trypanosomes in any bodily fluid
3 months	3 months ± 1 week	FA3 n₃=70 Fexi	 Patient alive with no evidence of trypanosomes in any bodily fluid (no lumbar puncture at 3 months unless Investigator suspects relapse) 	 Neurological signs or symptoms leading to use of rescue treatment 	• Evidence of trypanosomes in any bodily fluid
6 months	6 months ± 2 weeks	FA4 n₄=70 Fexi	 Patient alive with no evidence of trypanosomes in any bodily fluid and CSF WBC ≤ 20/µL 	 CSF WBC ≥ 50/µL (36) Neurological signs or symptoms leading to use of rescue treatment 	• Evidence of trypanosomes in any bodily fluid
			 If uncertain (CSF WBC between 20 and 50/µL), request additional visit in 1-3 months 		
12 months	12 months ± 4 weeks	FA5 n₅=70 Fexi	 Patient alive with no evidence of trypanosomes in any bodily fluid and CSF WBC ≤ 20/µL CSF WBS between 20 and 50/µL, and lower as compared to previous value(s) 	 CSF WBC ≥ 50/µL CSF WBC > 20/µL and higher as compared to previous value(s) Neurological signs or symptoms leading to use of rescue treatment 	• Evidence of trypanosomes in any bodily fluid

Protocol number DNDiFEX004 Version 4.0

DNDi / Fexinidazole

12 months	12	Interim	Patient alive	No evidence of	Evidence of

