9.8. Efficacy Analysis

9.8.1. Primary Efficacy Analysis

Primary Efficacy Endpoint

The primary efficacy endpoint is the outcome at 18 months. Outcome will be considered as a success if there is no evidence of trypanosomes in any bodily fluid and if the CSF WBC is $\leq 20/\mu$ L. Death and use of rescue treatment will be considered as a relapse, i.e. a failure. A patient who attends the 18-month visit or who is found again after an active search, who refused to undergo lumbar puncture but who has no signs or symptoms of HAT, and for whom the outcome was assessed as favourable at the latest assessment will be considered as a probable cure, i.e. a success, unless signs of relapse are detected on any assessment up to 24 months.

Primary Assessment Criterion

The primary assessment criterion is the success rate at 18 months.

Primary Test

The primary test is the Blackwelder non-inferiority test, based on the difference in the success rates and a margin of 13% (see Margin for "Acceptable Difference"; p 63).

Primary Measure of Size of Effect

The size of the treatment effect will be measured by the excess rate of success. The excess success rate is equal to the difference in the success rates between the two groups: size of effect = p_{fexi} - p_{NECT} . A negative success rate corresponds to a treatment effect in favour of NECT.

Margin for "Acceptable Difference"

The margin for an "acceptable difference" is set at $13\%^6$.

⁶ A survey was carried out by e-mail in the small population of local and international physicians who are experienced in treating patients with HAT, in order to assess the limit of an acceptable difference and the limit of an unacceptable difference in efficacy between an oral drug and NECT. Between the two limits, there is an "uncertainty zone". The median response for an unacceptable difference was 17% and the median response for an acceptable difference was 9%. A margin of 13% was chosen and is equal to the first tertile of the distribution of an unacceptable difference. It means that the unacceptable limit was above 13% for 2/3 of respondents, i.e. for 6/19 respondents, the unacceptable limit was below 13% and, for 12/19, the limit was above 13%. The margin of 13% is also at the mid-point between the median of an acceptable difference (9%) according to respondents and the median of an unacceptable difference (17%) for the same respondents (see results of the survey in Figure 4; p 108).

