** The choice of the limit for the difference is based on the rounded difference between melarsoprol and effornithine instead of NECT because more data are available on effornithine (n = 748). Consequently, the stopping rules are defined as a difference with regard to NECT significantly larger, i.e. worse, than the difference between melarsoprol and effornithine. x = See below time course of the response for melarsoprol, effornithine and NECT.

Δ "Responder" at 3 months is defined as patient alive with no evidence of trypanosomes in any bodily fluid, i.e. blood, lymph or CSF or no neurological signs or symptoms requiring rescue treatment.

"Favourable outcome" at 6 and 12 months is defined as patient alive with no evidence of trypanosomes in any bodily fluid and CSF WBC $\leq 20/\mu$ L CSF, or CSF WBC > 20 and $< 50/\mu$ L and reduced in relation to previous value(s). Relapse at 6 and 12 months is defined as evidence of trypanosomes in any bodily fluid, or CSF WBC $\geq 50/\mu$ L, or CSF WBC > 20 and $< 50/\mu$ L and increased in relation to previous value(s), or a change in treatment.

Table 6 – Study Schedule

Final version of protocol	June 2012		
Study treatments available	June 2012		
First patient first visit	October 2012		
Duration of enrolment period	24 months		
Duration of follow-up period	18 months (primary endpoint) – 24 months (follow-up)		
Last patient last visit	September 2016 (primary endpoint) – March 2017 (24-month follow-up)		
Final study report	December 2016 (primary endpoint) – June 2017 (follow-up)		

Table 7 – Expected Enrolment Rates (actual rates up to Q2 2013)

	Actual Enrolment	2015	
Study Sites	Q3 2012 – Q4 2014	Q1	Total per site
01 Bandundu	47	5	52
02 Vanga	61	5	66
03 Masi Manimba	82	4	86
04 Dipumba	51	3	54
05 Dingila	32	0	32
06 Batangafo	12	0	12
07 Mushie	19	4	23
08 Katanda	19	4	23
09 Isangi	31	4	35
10 Bagata	3	4	7
Cumulative Total	357	33	390

The forecast may be revised if new investigational sites are added.

[figure not shown]
Table 8 – Overall Organisation of the Study

Target countries	countries Democratic Republic of the Congo (RDC), Central African Repu (CAR)				
Target enrolment rate		Screened	Randomised		
	TOTAL	592	390		
Number of sites	At least 6 sites				
Number of patients	Up to 140 patients per site				
randomised per site					
Participation of a	An independent steering committee (ISC or DSMB) will be appointed				
DSMB	to look after safety issues.				

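### Table 2's 12-month row lists a CSF white-cell count of 20/µL or more as probable relapse, which triggers rescue, while the same row calls 20–50/µL and falling favourable

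*Protocol*

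**What the plan says.** Section 5.9 makes rescue the stated consequence of relapse: patients with evidence "of probable relapse at any time during follow-up will receive an alternative treatment for HAT". It then defines probable relapse at 6, 12 and 18 months by Table 2.

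For a patient without trypanosomes, the CSF count criteria in Table 2's 12-month row are:

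- **Favourable:** up to 20/µL, or between 20 and 50/µL "and lower as compared to previous value(s".
- **Uncertain:** above 20/µL with an increase that is not clinically significant, or any reason for which the investigator asks for an extra visit.
- **Probable relapse:** "CSF WBC ≥ 20/µL", or above 20/µL with a clinically significant increase.

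Under the table the protocol adds: "This classification will not be used directly for statistical purposes". Section 9.8.1, on the primary endpoint, says: "Death and use of rescue treatment will be considered as a relapse, i.e. a failure".

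Three other places give a limit of 50/µL. Table 2's own 6-month row uses ≥ 50/µL. The FA5 row of Table 1 (12 months) uses ≥ 50/µL, or above 20/µL and rising. The note to Table 5 counts as relapse at 6 and 12 months a count of 50/µL or more, or one above 20 and below 50/µL "and increased in relation to previous value(s), or a change in treatment".

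**The concern.** The probable-relapse cell carries no trend condition, so it covers every falling count of 20 to 50/µL that the favourable cell also covers. It also covers the modest rises that the uncertain cell sends to an extra visit. Nothing in section 5.9 says which cell takes precedence. Table 1 is headed as serving statistical purposes only, so Table 2 is the rule a site has for deciding on rescue.

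Two things are at stake. A patient whose CSF is clearing may be retreated without need. And because rescue counts as failure, the choice of cell can decide the 18-month outcome. The investigator makes that choice knowing the treatment arm.

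**Working it through.** **1. Apply each 12-month rule to the same counts.** The patient is parasite-free and no other disease explains the count.

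| 12-month count and trend | Table 2 favourable? | Table 2 probable relapse, as printed? | Table 1, FA5 row | Table 1, interim row |
|---|---|---|---|---|
| 20/µL, falling or rising | yes | yes | favourable | favourable |
| 30/µL, falling | yes | yes | favourable | probable relapse |
| 49/µL, falling | yes | yes | favourable | probable relapse |
| 50/µL, falling | yes | yes | in both cells | probable relapse |
| 51/µL, falling | no | yes | probable relapse | probable relapse |
| 30/µL, rising | no | yes (also uncertain if the rise is not clinically significant) | probable relapse | probable relapse |

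Every falling count from 20 to 50/µL is in two Table 2 columns at once, and exactly 20/µL is in both whatever its trend.

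**2. Which number was meant.** If ≥ 20/µL were sufficient, the second criterion in the same cell (above 20/µL with a significant increase) would add nothing. With ≥ 50/µL it has a purpose, and the row agrees with the 6-month row, the FA5 row and the Table 5 note. One overlap would remain, at exactly 50/µL and falling. The Table 5 note avoids it by writing below 50.

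**3. Route to the primary endpoint.** Table 2 is not used directly in the statistics, and the early-withdrawal clause in section 2.2.1 refers to Table 1. The link is rescue actually given: 30/µL and falling at 12 months → rescue under the ≥ 20 cell → failure under section 9.8.1, even if the 18-month count is 20/µL or less. Without rescue, the same patient with that 18-month count and no parasites is a success.

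**4. Size, as an illustration.** Inputs from section 9.1: success 94% on NECT and 89% on fexinidazole, margin 13%, 130 and 260 patients, one-sided 0.025.

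Power = Φ((0.13 − (pN − pF))/SE − 1.96), with SE = √(pN(1 − pN)/130 + pF(1 − pF)/260).

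The plan's own figure: SE = √(0.94×0.06/130 + 0.89×0.11/260) = 0.02847, and Φ(0.08/0.02847 − 1.96) = 80.2%, which reproduces the stated 80%.

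The documents give no share of patients in the contested group. Assume that a share d of each arm would have succeeded but is rescued because of the ≥ 20 cell:

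| d in both arms | Patients of 390 | pN / pF | SE | Power |
|---|---|---|---|---|
| 0 | 0 | 0.94 / 0.89 | 0.02847 | 80.2% |
| 0.5% | about 2 | 0.935 / 0.885 | 0.02931 | 77.9% |
| 1% | about 4 | 0.93 / 0.88 | 0.03012 | 75.7% |
| 2% | about 8 | 0.92 / 0.87 | 0.03164 | 71.5% |

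With equal d, a true 13-point difference stays at 13 points, so the same formula leaves the type I error unchanged.

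**The case against.** The strongest reply is that this is a one-digit slip which the row itself exposes. A careful investigator cannot apply ≥ 20/µL literally without ignoring the neighbouring cells, and nothing in the protocol shows that any site did so. The text also softens automatic rescue. The paragraph under Table 2 allows an extra visit before deciding on rescue, the uncertain cell accepts any reason for one, and section 6.4.5 requires a return visit within 1 to 3 months when the CSF count raises suspicion of relapse. All of this stands, and it limits the likely number of patients affected. It does not remove the conflict, because the printed rule still says that probable relapse will be treated and no text ranks the cells.

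A reader might also infer more than the documents support:

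- **That Table 1 as a whole calls these patients favourable.** Only the FA5 row does. The interim row and the 12-month definition in section 2.2.1 already count an unexplained value above 20/µL as failure, so the 12-month interim analysis is not affected above 20/µL.
- **That the planned comparison of 12- with 18-month success, and the validation of the prediction models, become circular.** That would need every site to read the cell literally and every such patient to be rescued. Some dependence exists under any rule that counts rescue as failure, including the corrected one.
- **That power falls much further because fexinidazole patients are affected more.** Converting 1% of fexinidazole patients and no NECT patients would give 67.6%, but no figure in the documents supports a difference between arms. The open label makes one possible and does not establish it.

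**Conclusion.** Table 2's 12-month row contradicts itself at a threshold that decides rescue, and section 9.8.1 carries the result into the primary endpoint. That much is certain from the text. That 50 was intended is almost certain. The size of the effect cannot be worked out from the documents. It depends on how many patients are at 20–50/µL and falling at 12 months, how many of them sites rescue under the ≥ 20 cell, and how many would otherwise have succeeded. If none, nothing changes; at 1% of both arms, power goes from 80.2% to about 76%. Equal conversion costs power without inflating the type I error, so it gives no ground to infer a false claim of non-inferiority. The correction should be made because it is cheap and concerns both patient care and the primary outcome.

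**What to change.** In Table 2, 12 months:

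- probable relapse: replace ≥ 20/µL by ≥ 50/µL;
- favourable: change the second criterion to above 20 and below 50/µL and lower than before, so that exactly 50/µL falls in one cell only. The FA5 row of Table 1 has the same edge and can take the same wording.

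Notify the sites. List every patient already rescued at 12 months with a count of 20–49/µL and falling, by arm, and keep them as failures in the primary analysis as section 9.8.1 requires. An analysis counting them as successes is optional, because their outcome without rescue cannot be observed.

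The cost is two table edits, a site notice and one listing; the sample size and primary rule are unchanged. The clinical downside is that rescue may come later for a true relapser whose count is 20–49/µL and still falling. The extra visit already provided for limits that delay.

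### The 12-month row of Table 2 sets probable relapse at a CSF WBC count of 20/µL where 50/µL is evidently meant, so an improving patient could be given rescue treatment and become a month-18 failure

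*Protocol*

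**What the plan says.** Protocol section 5.9 states that patients with proven relapse "or of probable relapse at any time during follow-up will receive an alternative treatment for HAT", and gives Table 2 as the definition of probable relapse at months 6, 12 and 18. In the 12-month row:

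- **Favourable** covers a patient without trypanosomes and with a count of at most 20/µL. It also covers "CSF WBS between 20 and 50/µL, and lower as compared to previous value(s").
- **Uncertain** covers a count above 20/µL whose increase is not clinically significant.
- **Probable relapse** starts with "CSF WBC ≥ 20/µL". The next bullet in the same cell is "CSF WBC > 20/µL and significant increase from a clinical standpoint in relation to prior value(s").

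A note under the table says the classification is not used directly for statistics. Section 9.8.1, on the primary endpoint, states: "Death and use of rescue treatment will be considered as a relapse, i.e. a failure".

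**The concern.** The first probable-relapse bullet takes in every count from 20/µL upward, whatever its direction. That absorbs the second favourable entry and the whole uncertain entry of the same row, and leaves the next bullet with nothing to do. An investigator reading the row has two contradictory instructions for a patient whose count is between 20 and 50/µL and coming down: leave alone, or retreat.

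The first consequence is for the patient, who may be given a second course of HAT treatment without need. The second is for the trial. Once rescue is given, the month-18 outcome is failure even if the count would have reached 20/µL or less by then. Table 2 applies to both arms. Under open-label care the contradiction could be resolved differently by arm, but nothing in the text says that it would be.

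**Working it through.** **1. The rules side by side (CSF WBC per µL, no trypanosomes found)**

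| Place | Use | 20–50 and falling | 20–50 and rising | 50 or more |
|---|---|---|---|---|
| Table 2, 12 months, as written | rescue | favourable **and** probable relapse | uncertain or probable relapse by clinical significance, **and** probable relapse by the first bullet | probable relapse |
| Table 1, 12 months, futility analysis 5 | futility | favourable | probable relapse | probable relapse |
| Table 5 footnote, 6 and 12 months | futility | favourable | relapse | relapse |
| Table 2, 6 months | rescue | uncertain, extra visit | uncertain, extra visit | probable relapse |
| Table 1 interim row and section 2.2.1, 12 months | interim endpoint | failure unless another disease explains the count | same | same |

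The Table 5 footnote is explicit for this visit: "Relapse at 6 and 12 months is defined as evidence of trypanosomes in any bodily fluid, or CSF WBC $\geq 50/\mu$ L", or a count in the 20–50 band that has increased.

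**2. Two test cases in the 12-month row of Table 2**

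- A count of 35/µL, lower than before: favourable by the second favourable entry, probable relapse by the first relapse bullet.
- A count of exactly 20/µL: favourable (at most 20) and probable relapse (at least 20).

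With 50 in place of 20, both conflicts disappear and the bullet requiring a significant increase regains its purpose.

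**3. Route to the primary endpoint**

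Table 2 classes the patient as probable relapse; section 5.9 then provides for alternative treatment; section 9.8.1 makes use of that treatment a failure at month 18. The interim endpoint is little affected, because section 2.2.1 and the interim row of Table 1 already count an unexplained value above 20/µL at month 12 as failure.

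**4. Size**

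Inputs from section 9.1: 260 fexinidazole and 130 NECT patients, expected success 89% and 94%, margin 13%, one-sided 0.025.

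Per patient: 1/260 = 0.38 points; 1/130 = 0.77 points.

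Power = Φ[(0.13 − (pN − pF))/SE − 1.96], with SE = √[pF(1 − pF)/260 + pN(1 − pN)/130].

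Planned case: SE = √(0.89 × 0.11/260 + 0.94 × 0.06/130) = 0.0285; 0.08/0.0285 = 2.81; Φ(2.81 − 1.96) = 80.2%. The protocol's 80% is reproduced.

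The protocol does not say how many patients would be affected, so the losses below are assumptions:

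| Points lost | Patients (fexinidazole / NECT) | Power, same loss in both arms | Power, loss in fexinidazole only |
|---|---|---|---|
| 1 | 2.6 / 1.3 | 75.7% (88% vs 93%) | 67.6% (88% vs 94%) |
| 2 | 5.2 / 2.6 | 71.5% (87% vs 92%) | 53.0% (87% vs 94%) |
| 3 | 7.8 / 3.9 | 67.7% (86% vs 91%) | 38.6% (86% vs 94%) |

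The NECT patient counts apply only to the both-arms column. The last column is an upper bound that the text does not imply.

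**The case against.** The slip itself is hard to dispute; the case on the other side concerns its consequences.

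- **Safeguards.** The row has a specific favourable entry for this patient. The note under Table 2 lets the team class a doubtful case as uncertain and call an extra visit before deciding on rescue. Section 6.4.5 requires a return visit within 1 to 3 months when relapse is suspected on the count. This stands as far as it goes: retreatment is possible, not prescribed. Neither provision says which threshold governs, at the first visit or at the return.
- **The statistics note and Table 1.** Table 2 is not used directly for analysis. Section 2.2.1 ties earlier unfavourable outcomes and withdrawal for probable relapse to Table 1, where a falling 20–50 count is favourable in the 12-month futility row. This narrows the route to one step, actual use of rescue treatment, but section 9.8.1 keeps that step open.
- **50/µL is not universal.** Of the 12-month rules, only the two futility ones use it; the interim endpoint uses more than 20/µL. That is correct, but the interim rule decides an endpoint, not treatment. It also cannot explain a row that calls 20 to 50 and falling favourable.
- **The power figures have no anchor.** A success is lost only if the patient is in the band, is retreated, and would otherwise have succeeded at month 18. None of these probabilities is given. The starting point is also generous: section 9.11 applies a Pocock adjustment to the final test, and the text with Figure 3 gives a one-sided error of 1.45%, at which the same formula gives 73.5%. The figures are therefore only illustrative, and the finding does not rest on them.
- **Timing.** This version cites a 2016 publication, while Table 7 ends enrolment in the first quarter of 2015. Most month-12 visits may already have taken place. That limits what reissuing the table can prevent and makes the listing of patients already retreated more important.

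**Conclusion.** The concern holds. The 12-month threshold of 20/µL in Table 2 is wrong as written: it contradicts two other cells of its row, makes the next bullet redundant, and departs from the 12-month futility definitions in Tables 1 and 5. It is more than a clerical slip because it triggers treatment that in turn decides the primary endpoint.

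The effect is confined to the month-18 endpoint and to unnecessary retreatment. Its size cannot be determined from the protocol. Only the per-patient weights are firm; the fall in power depends on the assumed 1 to 3 points lost and, for the larger figures, on the whole loss falling on fexinidazole. It should be fixed, but it does not undermine the design.

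**What to change.** In the 12-month row of Table 2:

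1. Change the first probable-relapse bullet to a count of 50/µL or more.
2. Define the intermediate band as more than 20 and less than 50/µL and make it mutually exclusive. Falling is favourable. Unchanged, or an increase that is not clinically significant, is uncertain, with a return visit in 1 to 3 months. A clinically significant increase is probable relapse. Changing the number alone would leave an unchanged count without a class, and a count of 50/µL or more with a non-significant increase in two.
3. Send the corrected table to the sites.
4. At the blinded data review, list every patient retreated at month 12 with 20 to 50/µL and no trypanosomes. Section 5.9 has rescue treatment recorded in the Comments section of the e-CRF, so the listing must be drawn from there.

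The cost is one number, the band limits, a clarification to sites and one listing. No procedure, visit or sample-size figure changes.
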